7. ADVERSE EVENTS: LIST AND REPORTING REQUIREMENTS

Adverse event (AE) monitoring and reporting is a routine part of every clinical trial. The following list of AEs (Section 7.1) and the characteristics of an observed AE (Section 7.2) will determine whether the event requires expedited reporting via Medwatch Forms **in addition** to routine reporting.

7.1 Expected Toxicities

7.1.1 Adverse Events List(s)

7.1.1.1 Adverse Event List(s) for Cisplatin

Please see the package insert for all toxicities associated with CISPLATIN. Below is a listing of the most commonly seen toxicities.

Nephrotoxicity: Dose-related and cumulative renal insufficiency, including acute renal failure, is the major dose-limiting toxicity of PLATINOL. Renal toxicity has been noted in 28% to 36% of patients treated with a single dose of 50 mg/m². It is first noted during the second week after a dose and is manifested by elevations in BUN and creatinine, serum uric acid and/or a decrease in creatinine clearance. Renal toxicity becomes more prolonged and severe with repeated courses of the drug. Elderly patients may be more susceptible to nephrotoxicity. Impairment of renal function has been associated with renal tubular damage. The administration of CISPLATIN using a 6-8-hour infusion with intravenous hydration, and mannitol has been used to reduce nephrotoxicity. However, renal toxicity still can occur after utilization of these procedures.

Ototoxicity: Ototoxicity has been observed in up to 31% of patients treated with a single dose of CISPLATIN 50 mg/m² and is manifested by tinnitus and/or hearing loss in the high frequency range (4000 to 8000 Hz). Decreased ability to hear normal conversational tones may occur. Deafness after the initial dose of CISPLATIN has been reported. Ototoxic effects may be more severe in children receiving CISPLATIN. Hearing loss can be unilateral or bilateral and tends to become more frequent and severe with repeated doses. Ototoxicity may be enhanced with prior or simultaneous cranial irradiation. It is unclear whether CISPLATIN-induced

ototoxicity is reversible. Ototoxic effects may be related to the peak plasma concentration of CISPLATIN. Careful monitoring of audiometry is recommended prior to initiation of therapy and prior to subsequent doses of CISPLATIN. Vestibular toxicity has also been reported. Ototoxicity may become more severe in patients being treated with other drugs with nephrotoxic potential.

Hematologic: Myelosuppression occurs in 25% to 30% of patients treated with CISPLATIN. The nadirs in circulating platelets and leukocytes occur between days 18 to 23 (range 7.5 to 45) with most patients recovering by day 39 (range 13 to 62). Leukopenia and thrombocytopenia are more pronounced at higher doses (>50 mg/m 2). Anemia (decrease of 2 g hemoglobin/100 mL) occurs at approximately the same frequency and with the same timing as leukopenia and thrombocytopenia. Fever and infection have also been reported in patients with neutropenia. Potential fatalities due to infection (secondary to myelosuppression) have been reported. Elderly patients may be more susceptible to myelosuppression. In addition to anemia secondary to myelosuppression, a Coombs' positive hemolytic anemia has been reported. In the presence of cisplatin hemolytic anemia, a further course of treatment may be accompanied by increased hemolysis and this risk should be weighed by the treating physician. The development of acute leukemia coincident with the use of CISPLATIN has been reported. In these reports, CISPLATIN was generally given in combination with other leukemogenic agents.

Gastrointestinal: Marked nausea and vomiting occur in almost all patients treated with CISPLATIN, and may be so severe that the drug must be discontinued. Nausea and vomiting may begin within 1 to 4 hours after treatment and last up to 24 hours. Various degrees of vomiting, nausea and/or anorexia may persist for up to 1 week after treatment. Delayed nausea and vomiting (begins or persists 24 hours or more after chemotherapy) has occurred in patients attaining complete emetic control on the day of CISPLATIN therapy. Diarrhea has also been reported.

OTHER TOXICITIES

Vascular toxicities: Vascular toxicities coincident with the use of CISPLATIN in combination with other antineoplastic agents have been reported. The events are clinically heterogeneous and may include myocardial infarction, cerebrovascular accident, thrombotic microangiopathy (hemolytic-uremic syndrome [HUS]), or cerebral arteritis. Various mechanisms have been proposed for these vascular complications. There are also reports of Raynaud's phenomenon occurring in patients treated with the combination of bleomycin, vinblastine with or without CISPLATIN. It has been suggested that hypomagnesemia developing coincident with the use of CISPLATIN may be an added, although not essential, factor associated with this event. However, it is currently unknown if the cause of Raynaud's phenomenon in these cases is the disease, underlying vascular compromise, bleomycin, vinblastine, hypomagnesemia, or a combination of any of these factors.

Serum Electrolyte Disturbances: Hypomagnesemia, hypocalcemia, hyponatremia, hypokalemia, and hypophosphatemia have been reported to occur in patients treated with CISPLATIN and are probably related to renal tubular damage. Tetany has been reported in patients with hypocalcemia and hypomagnesemia. Generally, normal serum electrolyte levels are restored by administering supplemental electrolytes and discontinuing CISPLATIN. Inappropriate antidiuretic hormone syndrome has also been reported.

Hyperuricemia: Hyperuricemia has been reported to occur at approximately the same frequency as the increases in BUN and serum creatinine. It is more pronounced after doses >50 mg/m², and peak levels of uric acid generally occur between 3 to 5 days after the dose. Allopurinol therapy for hyperuricemia effectively reduces uric acid levels.

Neurotoxicity: Neurotoxicity, usually characterized by peripheral neuropathies, has been reported. The neuropathies usually occur after prolonged therapy (4 to 7 months); however, neurologic symptoms have been reported to occur after a single dose. Although symptoms and signs of CISPLATIN neuropathy usually develop during treatment, symptoms of neuropathy may begin 3 to 8 weeks after the last dose of CISPLATIN. CISPLATIN therapy should be discontinued when the symptoms are first observed. The neuropathy, however, may progress further even after stopping treatment. Preliminary evidence suggests peripheral neuropathy may be irreversible in some patients. Elderly patients may be more susceptible to peripheral neuropathy. Lhermitte's sign, dorsal column myelopathy, and autonomic neuropathy have also been reported. Loss of taste, seizures, leukoencephalopathy, and reversible posterior leukoencephalopathy syndrome (RPLS) have also been reported.

Muscle cramps: Muscle cramps, defined as localized, painful, involuntary skeletal muscle contractions of sudden onset and short duration, have been reported and were usually associated with patients receiving a relatively high cumulative dose of CISPLATIN and with a relatively advanced symptomatic stage of peripheral neuropathy.

Ocular Toxicity: Optic neuritis, papilledema, and cerebral blindness have been reported in patients receiving standard recommended doses of CISPLATIN. Improvement and/or total recovery usually occurs after discontinuing CISPLATIN. Steroids with or without mannitol have been used; however, efficacy has not been established. Blurred vision and altered color perception have been reported after the use of regimens with higher doses of CISPLATIN or greater dose frequencies than recommended in the package insert. The altered color perception manifests as a loss of color discrimination, particularly in the blue-yellow axis. The only finding on funduscopic exam is irregular retinal pigmentation of the macular area.

Anaphylactic-Like Reactions: Anaphylactic-like reactions have been reported in patients previously exposed to CISPLATIN. The reactions consist of facial edema, wheezing, tachycardia, and hypotension within a few minutes of drug administration.

Reactions may be controlled by intravenous epinephrine with corticosteroids and/or antihistamines as indicated. Patients receiving CISPLATIN should be observed carefully for possible anaphylactic-like reactions and supportive equipment and medication should be available to treat such a complication.

Transient liver function test abnormalities, cardiac abnormalities, hiccups, elevated serum amylase, rash, alopecia, malaise, asthenia, and dehydration have been reported.

Local soft tissue toxicity has been reported following extravasation of CISPLATIN. Severity of the local tissue toxicity appears to be related to the concentration of the CISPLATIN solution.

Infusion of solutions with a CISPLATIN concentration >0.5 mg/mL may result in tissue cellulitis, fibrosis, necrosis, pain, edema, and erythema.

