1. OBJECTIVES

1.1 Primary Objectives

1.1.1 Rate of grade 3-5 cisplatin-related adverse events occurring within 90 days of initiation of concurrent radiation and chemotherapy including:

- nausea/vomiting
- ototoxicity
- nephrotoxicity
- neutropenia
- thrombocytopenia

1.1.2 Hypothesis: Patients with locally advanced non-nasopharyngeal SCCHN treated with weekly cisplatin (40 mg/m² weekly for 7 doses) with radiation (RT) will have fewer cisplatin-related acute toxicities as compared to those receiving every three-week cisplatin (100 mg/m² for 3 doses) with radiation in the following cohorts:

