- creatinine clearance $\geq 60 \text{ mL/min}/1.73 \text{ m}^2$ for patients with creatinine levels above institutional normal

OR

- 3.1.9 No prior chemotherapy for the **current** locally advanced SCCHN is allowed. Prior radiation or chemotherapy for a previous head and neck cancer is allowed provided full dose cisplatin and radiation can be delivered to the patient in this clinical trial and provided the patient is in remission from the prior head and neck cancer, and can undergo full dose radiation and chemotherapy for the current primary head and neck cancer.
- 3.1.10 Cisplatin and radiation are known teratogens. For this reason, women of child-bearing potential and men must agree to use adequate contraception (hormonal or barrier method of birth control; abstinence) prior to study entry, throughout the duration of active treatment and for 4 months after completion of chemotherapy and radiation. Should a woman become pregnant or suspect she is pregnant while she or her partner is participating in this study, she should inform her treating physician immediately. Men treated or enrolled on this protocol must also agree to use adequate contraception prior to the study, for the duration of active study treatment, and for 4 months after completion of chemotherapy and radiation (both induction and definitive) administration.

- 3.1.11 Ability to understand and the willingness to sign a written informed consent document.

3.2 **Exclusion Criteria**

- 3.2.1 Patients who have had chemotherapy or radiotherapy within 4 weeks (6 weeks for nitrosoureas or mitomycin C) prior to entering the study or those who have not recovered from adverse events due to agents administered more than 4 weeks earlier.
- 3.2.2 Patients who are receiving any other investigational agents.
- 3.2.3 History of allergic reactions attributed to compounds of similar chemical or biologic composition to cisplatin.
- 3.2.4 Patients with greater than grade 2 hearing loss.
- 3.2.5 No other prior malignancy is allowed except for the following: head and neck cancer in remission, adequately treated basal cell or squamous cell skin cancer, in situ cervical cancer, adequately treated previous Stage I or II cancer from which the patient is currently in complete remission or other cancer from which the patient has been disease-free for 2 years.
- 3.2.6 Patients with nasopharynx or salivary gland primary site.

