5. TREATMENT PLAN

5.1 Enrollment and Screening Process

Prior to any study-required tests, subjects must first provide written informed consent to participate in this study. All lab tests should be completed within 3 weeks prior to registration: Complete history, physical examination, and evaluation of ECOG Performance Status. CBC; serum chemistry tests to include alkaline phosphatase, creatinine, electrolytes, AST (SGOT), and total bilirubin. All radiographic studies (CT with contrast or MRI of the head and neck region, CT of chest or chest x-ray) should be completed within: a) Cohort 1: 6 weeks prior to registration, OR b) Cohort 2: within 8 weeks prior to registration.

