6. DOSING DELAYS/DOSE MODIFICATIONS

Dose Modifications for cisplatin, days 8 and beyond

Dose Level	Every 3-week Cisplatin	Weekly Cisplatin
-2	50 mg/m ² every 3 weeks	20 mg/m ² weekly
-1	75 mg/m ² every 3 weeks	30 mg/m ² weekly
0	100 mg/m ² every 3 weeks	40 mg/m ² weekly

No more than two dose reductions are allowed and no re-escalation of dosing is allowed. If a subject requires more than two dose reductions, cisplatin will be permanently discontinued. Every effort will be made to complete all planned doses of chemotherapy, with dose modifications listed below, however, no chemotherapy will be given after completion of radiation.

Neutropenia. If on the day of scheduled treatment with cisplatin the absolute neutrophil count (ANC) is < 1000, hold treatment until ANC ≥ 1000 then treat at 100% dose.

Neutropenic fever. If grade 3 or 4 neutropenic fever occurs, defined as temperature ≥38.5°C [101°F] sustained for more than one-hour concomitant with ANC <500/mm³, hold cisplatin until ANC >1000, and reduce subsequent cisplatin doses by 1 dose level.

Thrombocytopenia. If on the day of scheduled treatment with cisplatin the platelet count is <75,000 hold treatment until platelets are >75,000 then treat at 100% dose.

Thrombocytopenia that results in significant bleeding. If grade 3 or 4 thrombocytopenia occurs with bleeding that is clinically significant, as determined by the treating physician, hold cisplatin until platelets are >75,000 and reduce subsequent cisplatin doses by 1 dose level.

Neurotoxicity. If grade 3 or greater neurotoxicity, including neuropathy occurs, hold cisplatin until resolution to less than or equal to grade 1. Resume cisplatin at one dose level lower. If grade 3 or greater neurotoxicity persist after two dose reductions or does not improve after 14 days, discontinue cisplatin.

Renal Toxicity. If a subject's creatinine clearance falls below 50 ml/min, cisplatin should be held for that dose and should only be restarted once the creatinine clearance improves to >50 ml/min. Subsequent doses should be dose reduced by one dose level. If Cr Cl does not recover to >50 ml/min after 14 days, discontinue cisplatin.

Mucositis: If grade 4 mucositis occurs, hold cisplatin until resolution to less than or equal to grade 2 and reduce subsequent cisplatin doses by 1 dose level.

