Ototoxicity or tinnitus: If grade 3 or greater ototoxicity or tinnitus occurs, hold cisplatin until resolution to less than or equal to grade 2 and reduce subsequent cisplatin doses by 1 dose level. If grade 3 or greater hearing loss or tinnitus persist after two dose reductions or does not improve after 14 days, discontinue cisplatin.

Dose Modifications for Other Toxicity: In the event of any other (except nausea and vomiting) grade 3 or 4 non-hematologic toxicity not discussed above, hold all protocol treatment and discuss with the PI. For treatment or dose modification related questions, please contact the PI.

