13. STATISTICAL CONSIDERATIONS

13.1 Study Design/Endpoints

This is a 1:1 randomized, unblinded phase II trial of radiation with cisplatin weekly versus every three weeks for patients with locally advanced non-nasopharyngeal SCCHN. The primary endpoint is cisplatin-related acute toxicities (within the first 90 days after the start of radiation). These include all grade 3-5 events of nausea/vomiting, ototoxicity, nephrotoxicity, and neutropenia and thrombocytopenia. Secondary objectives include clinical outcomes (2-year local control rates, OS, PFS, response), additional toxicity outcomes (rates of dysphagia, dry mouth, and skin, other acute and late events according to CTCAE), correlates (oxidative stress markers), and quality of life outcomes (FACTHN, FACTCOG).

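### Grade 3-5 ototoxicity counts toward the primary endpoint, but no hearing assessment is scheduled beyond general adverse event evaluation, and the only test named is an optional pre-dose audiogram tied to each arm's dosing schedule

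*Combined protocol and SAP*

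**What the plan says.** Section 1.1.1 sets the primary objective as "Rate of grade 3-5 cisplatin-related adverse events occurring within 90 days of initiation of concurrent radiation and chemotherapy including" five named toxicities, ototoxicity among them. Section 13.1 repeats the list: "These include all grade 3-5 events of nausea/vomiting, ototoxicity, nephrotoxicity, and neutropenia and thrombocytopenia".

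Two other rules depend on a hearing grade. Exclusion 3.2.4 removes "Patients with greater than grade 2 hearing loss". Section 6 states: "If grade 3 or greater ototoxicity or tinnitus occurs, hold cisplatin until resolution to less than or equal to grade 2".

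Screening in 5.1 asks for "Complete history, physical examination, and evaluation of ECOG Performance Status", blood tests and imaging, with no hearing item. The section 10 calendar has no hearing row or footnote. Its adverse event row starts in week 1 and runs into follow-up in both arms, graded by CTCAE version 4.0 (7.2). Section 12.1.1 sends readers to that calendar for data reporting requirements.

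The only hearing test named anywhere is in the cisplatin toxicity list at 7.1.1.1: "Careful monitoring of audiometry is recommended prior to initiation of therapy and prior to subsequent doses of CISPLATIN". Nothing calls for a test after the last dose.

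**The concern.** A component of the primary endpoint should be looked for equally hard, and at the same times, in both arms. That matters most in an unblinded trial. Here the calendar leaves the effort unspecified, and the one method in the text follows the dosing schedule, which is exactly what differs between the arms. A clinic that follows the advice tests weekly-arm patients more often, and it leaves a larger share of the three-weekly dose untested.

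Two further gaps follow. Without a recorded pre-study grade, 3.2.4 cannot be checked from the data. Without a dated assessment between the last dose and day 90, hearing loss from the final dose may be recorded later and its onset reconstructed afterwards.

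**Working it through.** **Planned power.** Section 13.2 gives 36 per arm, 80% v 50%, Fisher's exact test, one-sided 0.05, and 80% power. Summing the two binomial distributions over all tables with one-sided p ≤ 0.05 gives 80.9%, so the stated figure reproduces.

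**Test counts if the 7.1.1.1 advice is followed.** Dose days are from 5.2.2 and the 30-35 fractions at five per week from 5.3.1. Section 6 adds that "no chemotherapy will be given after completion of radiation". Without breaks, 30 fractions end on day 40-42, so there is no day-43 dose; 31 fractions end on day 43 and 35 on day 47-49.

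| Radiation | Tests, weekly v three-weekly | Last test | Dose still to come after it (mg/m²) |
|---|---|---|---|
| 31-35 fractions | 7 v 3 | day 43 in both | 40/280 = 14% v 100/300 = 33% |
| 30 fractions | 6 v 2 | day 36 v day 22 | 40/240 = 17% v 100/200 = 50% |

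**Contacts between the last dose and day 90.** The post-treatment examination has no day. The restaging scan may be up to 8 weeks after radiation, so its latest date is day 40 + 56 = 96 to day 49 + 56 = 105. The 3-month questionnaire, taking 3 months as day 91, has the window 91 ± 42 = day 49 to 133, and the forms in Appendices B and C have no hearing item. Each may fall before day 90; none has to.

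**Direction.** More tests in the weekly arm raise its count. A larger untested dose share lowers the three-weekly count. Both shrink the observed difference.

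**Effect of a shift in the composite rate.** These are assumed shifts in the composite, not in ototoxicity detection (same exact test, 36 per arm):

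| Shift (points) | Arm 1 lower only | Arm 2 higher only | Both lower |
|---|---|---|---|
| 1 | 78.0% | 78.3% | 80.6% |
| 2 | 75.0% | 75.6% | 80.4% |
| 3 | 71.8% | 72.7% | 80.2% |
| 5 | 65.1% | 66.4% | 79.9% |

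**How far ototoxicity can move the composite.** A missed case matters only in a patient with no other qualifying event. Let *r* be the grade 3-5 ototoxicity rate in Arm 1 and *m* the share missed. With independent components, the chance of no other event is 0.20/(1 − *r*), and the loss is *r* × *m* × 0.20/(1 − *r*). The documents give no *r*, so a range is shown:

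- *r* = 5%, all missed: 0.05 × 0.20/0.95 = 1.1 points; power 77.9%.
- *r* = 10%, half missed: 0.05 × 0.20/0.90 = 1.1 points; power 77.7%.
- *r* = 10%, all missed: 0.10 × 0.20/0.90 = 2.2 points; power 74.3%.
- *r* = 20%, all missed: 0.20 × 0.20/0.80 = 5.0 points; power 65.1%.

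A 5-point shift therefore needs a 20% rate with every case missed in Arm 1 and none in Arm 2.

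**The case against.** The strongest reply is that the audiometry line is not a trial procedure. It sits in a toxicity list that refers readers to the package insert, and the protocol departs from that list elsewhere. The list mentions a 6-8-hour infusion, while the trial gives 1 hour. It says to stop cisplatin at the first neuropathy symptoms, while section 6 holds at grade 3 and resumes one level lower. The method the trial adopts is CTCAE adverse event evaluation, on one calendar row for both arms, with 2 years of toxicity follow-up (5.6) and onset times listed (13.4). Section 13.6 also promises accurate endpoint collection on the eCRFs, which are not in the documents and may already hold a hearing item.

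Most of this stands. A reader might infer that ototoxicity goes unmeasured, or that the trial requires 7 tests against 3. Neither is supported: adverse event evaluation covers hearing in both arms, and the counts apply only where staff take up the advice. *None after the last dose* is true of audiometry, not of adverse event recording. Whether extra audiograms change grade 3-5 counts also depends on CTCAE hearing criteria that the documents do not reproduce.

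What remains is that the calendar gives no hearing item, no pre-study grade and no fixed contact by day 90. Optional use of an arm-dependent test makes the effort vary by clinician and arm.

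**Conclusion.** The point holds as a gap in even ascertainment of one primary component. It is worth fixing because the fix is cheap. It is not a demonstrated bias.

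Where the advice is followed, the likely effect is against the weekly arm and on power. On the illustrative assumption of a 10% rate, independent components and half the cases missed in Arm 1 only, power is about 77.7% against 80.9% planned. Equal under-detection in both arms costs about 1 point or less, even at a 5-point shift. Larger losses need assumptions that no document supports.

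A reader might also infer a raised false-positive rate in favour of weekly dosing. The documents do not support that. It needs under-detection in the weekly arm, which is opposite to the effect of more frequent testing there. The only route is conjecture: that unblinded staff look harder in Arm 1 because of the trial hypothesis or because 7.1.1.1 says "Ototoxic effects may be related to the peak plasma concentration of CISPLATIN". The same could be said of any unblinded adverse event endpoint.

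**What to change.** In section 10, add one row, *hearing/tinnitus CTCAE v4.0 grade*, in both arms at the existing pre-study, week 1, week 4, week 7 and post-treatment examinations. Require the post-treatment grade after the last cisplatin dose and no later than day 90 from the start of chemoradiation. Use the pre-study grade to apply 3.2.4.

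Replace the per-dose audiometry advice in 7.1.1.1 with a statement that any audiometry used to grade the endpoint is done at these same calendar times in both arms. Audiograms prompted by symptoms still count, and the primary analysis does not change. If the eCRFs already hold such an item, only the calendar needs aligning.

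The cost is one graded item at five examinations that already exist, with no new procedure. Some post-treatment visits would move earlier, and some high-frequency loss would still be missed without audiometry.

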5.2 Cisplatin Administration

Treatment will be administered on an inpatient or outpatient basis. Reported adverse events and potential risks are described in Section 7. Appropriate dose modifications are described in Section 6. No investigational or commercial agents or therapies other than those described below may be administered with the intent to treat the patient's malignancy.

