5.2.2 Cisplatin Dosing

Use the actual body weight as long as the BSA is ≤ 2.3 . If the BSA is > 2.3 , recalculate using the adjusted body weight, and use the recalculated BSA to determine the dose with no cap.

Estimate Ideal body weight in (kg)

Males: IBW = 50 kg + 2.3 kg for each inch over 5 feet

Females: IBW = 45.5 kg + 2.3 kg for each inch over 5 feet

Adjusted body weight

$$AjBW = IBW + 0.4(ABW - IBW)$$

Arm 1 – Conventional fractionation plus every 3-week cisplatin

Patients will receive cisplatin (100 mg/m²) administered intravenously over 1 hour on days 1, 22, and 43 of the treatment course, relative to the initiation of radiation.

Arm 2 – Conventional fractionation plus weekly cisplatin

Patients will receive cisplatin (40 mg/m²) administered intravenously over 1 hour on days 1, 8, 15, 22, 29, 36, and 43 of the treatment course, relative to the initiation of radiation.

Premedication: Arms 1 & 2

Suggested premedication: include aprepitant (intravenous or oral), ondansetron, dexamethasone and either promethazine or prochlorperazine, per institutional standard. This trial endorses the NCCN guidelines for anti-emetic prophylaxis.

Pre- and Post-hydration: Arms 1 & 2

Patients must receive vigorous hydration and diuresis. A suggested regimen is: pre-hydration with a 1 liter of normal saline with electrolyte supplementation (e.g. potassium, magnesium) per standard of care, over 2 hours i.v. immediately prior to cisplatin. Then cisplatin 100 mg/m² in 500 ml normal saline is administered over 1 hour. Following cisplatin infusion, an additional 1 liter of normal saline with electrolyte supplementation (e.g. potassium, magnesium) per standard of care, given post-hydration over 2 hours.

Please see Section 6.0 for all dose modifications of cisplatin.

5.3 **Radiation Therapy**

All radiation therapy is considered standard of care, and toxicities and dose modifications will be made by the treating physician based on institutional standards. The guidelines below are recommended practice but may be modified at the discretion of the treating radiation oncologist.

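### Section 7.1.1.1 directs that cisplatin be stopped at the onset of neuropathy symptoms, which contradicts the Section 6 neurotoxicity rule, and no text qualifies it

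*Combined protocol and SAP*

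**What the plan says.** Two sections speak to what happens to cisplatin when a patient develops neuropathy.

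- Section 7.1.1.1, in the neurotoxicity paragraph of the cisplatin adverse event list: "CISPLATIN therapy should be discontinued when the symptoms are first observed". The sentence names no grade and does not say whether treatment may be resumed.
- Section 6, under neurotoxicity: "If grade 3 or greater neurotoxicity, including neuropathy occurs, hold cisplatin until resolution to less than or equal to grade 1". It continues: "Resume cisplatin at one dose level lower". Discontinuation comes later: "If grade 3 or greater neurotoxicity persist after two dose reductions or does not improve after 14 days, discontinue cisplatin".

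Other text bears on how the two sections relate. Section 5.2 says of risks, "Reported adverse events and potential risks are described in Section 7", and of dosing changes, "Appropriate dose modifications are described in Section 6". Section 5.2.2 adds: "Please see Section 6.0 for all dose modifications of cisplatin". Section 7.1.1.1 refers to the package insert and introduces itself with: "Below is a listing of the most commonly seen toxicities".

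**The concern.** An investigator who sees tingling or numbness of low grade finds an instruction to stop cisplatin in one section and no required action in the other. An investigator whose patient has recovered from a grade 3 episode finds a stop in one and a reduced-dose restart in the other.

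The main stake is patient safety. The same paragraph of Section 7.1.1.1 says that neuropathy can worsen after cisplatin is stopped and may be irreversible in some patients, so the protocol should not leave staff to choose between two instructions. The second stake is consistency of treatment. The trial is unblinded, Section 5.2.1 aims for at least 200 mg/m² in every patient, and Section 6 asks for every effort to complete the planned doses. Uneven stopping practice would work against both aims.

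**Working it through.** The plan gives no figure on this point to reproduce. The check is a comparison of texts, followed by simple arithmetic to show scale.

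**Step 1: the same patient under each section.**

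| Situation | Section 7.1.1.1 | Section 6 |
|---|---|---|
| Neuropathy symptoms, grade 1 or 2 | Discontinue | No action specified |
| Grade 3 or greater, recovering to grade 1 or less | Discontinue | Hold, then resume one dose level lower |
| Grade 3 or greater, persisting after two reductions or not improved after 14 days | Discontinue, already at onset | Discontinue |

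The two agree only in the third row, and there they differ in timing. In the first two rows they cannot both be followed.

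**Step 2: does the protocol settle which prevails?** Sections 5.2 and 5.2.2 give dose modification to Section 6 and description of risks to Section 7. The opening of Section 7 ties its adverse event list to deciding on expedited reporting. This makes Section 6 the section an investigator would naturally follow. No sentence, however, says that Section 6 takes precedence over the stopping instruction in Section 7.1.1.1, and nothing there limits that instruction or refers back to Section 6.

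**Step 3: is the sentence just description?** The list contains a few practice statements, for example on audiometry and on observation for anaphylactic-like reactions. On stopping the drug, its other remarks are of a different kind. The gastrointestinal paragraph describes how severe vomiting can become, and the paragraph on hemolytic anemia leaves further treatment to the physician's judgment. The neuropathy sentence is the only one that directs a stop without condition.

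**Step 4: largest possible difference for one patient.** Inputs are the doses in Section 5.2.1 and the dose levels in Section 6. The case is symptoms after dose 1, assuming under Section 6 that no later dose is missed and no second reduction is needed.

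- Every-three-week arm, stopped after dose 1: 100 mg/m². Section 6 at grade 1 or 2: 3 × 100 = 300 mg/m². Section 6 after recovery from grade 3: 100 + 2 × 75 = 250 mg/m².
- Weekly arm, stopped after dose 1: 40 mg/m². Section 6 at grade 1 or 2: 7 × 40 = 280 mg/m². Section 6 after recovery from grade 3: 40 + 6 × 30 = 220 mg/m².

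These are upper bounds on the gap. Later onset, a missed dose or a second reduction narrows it.

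**Step 5: the route to the primary endpoint.** Sections 1.1.1 and 13.1 count grade 3-5 nausea/vomiting, ototoxicity, nephrotoxicity, neutropenia and thrombocytopenia. Neuropathy is not among them. The only route is through lower exposure, since Section 7.1.1.1 describes renal and hearing toxicity as worsening with repeated dosing. One patient whose endpoint status changed this way would move an arm of 36 by 1/36 = 2.8 percentage points, against a planned difference of 80 − 50 = 30 points. How many such patients there would be is not given. Section 7.1.1.1 places neuropathy usually at 4 to 7 months of therapy, while Section 5.5 plans 7 weeks. It also reports symptoms after a single dose, so the number need not be zero.

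**The case against.** The strongest reply is that the protocol has already divided the work. Section 5.2.2 refers the reader to Section 6 for every cisplatin dose modification. Section 6 has a dedicated neurotoxicity rule with a trigger, a hold, a reduction and a stopping criterion. It also directs dose-modification questions to the principal investigator. Section 7.1.1.1 is a toxicity list, and Section 8 describes it the same way. An investigator who follows the cross-references arrives at one rule.

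Most of this stands. A reader might infer that two stopping rules of equal standing are in force, and the documents do not support that: Section 6 is the natural operative rule. But a cross-reference to one section does not cancel an unqualified instruction printed in another.

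A further reply is that Section 5.5 already lets treatment end for an unacceptable adverse event or on the investigator's judgment, so some variation below grade 3 would remain in any case. That is true. It also means that an investigator who relied on Section 7.1.1.1 could stop without an evident deviation, and Section 5.7 then removes from study any patient who meets a Section 5.5 criterion.

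A reader might also take Section 7.1.1.1 to require a permanent stop. It does not say so. Section 6 does use that term, for patients who would need more than two reductions, so the difference in wording should not be read away.

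**Conclusion.** The contradiction is real. It covers grade 1-2 neuropathy and grade 3 or greater neuropathy that recovers. It is mainly a patient-safety and consistency problem in the treatment text, and it does not touch randomization, sample size or the analysis plan.

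A reader might infer a threat to the primary comparison. The documents do not support that. Neuropathy is not a counted event, no frequency within 7 weeks is given, and both sentences apply to both arms. The weekly arm has seven dosing visits against three, so there are more occasions to apply either instruction, but nothing shows that stopping would differ by arm. Any effect is indirect and unquantified. It is probably small, on the assumption that the stated usual onset of 4 to 7 months holds for these patients. The dose gaps shown are extreme cases for a single patient and do not estimate a trial-level effect.

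No view is taken on which instruction is clinically right.

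**What to change.** Reconcile the neurotoxicity paragraph of Section 7.1.1.1 with the neurotoxicity rule in Section 6, and state in Section 7.1.1.1 which section governs discontinuation of cisplatin for neurotoxicity. Which clinical rule to keep is for the sponsor to decide.

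The cost is about one sentence, carried through the amendment review described in Section 4.1. If the sponsor instead changes the rule in Section 6, that paragraph needs editing as well. Neither route changes the sample size, the endpoint definition or the planned analysis.
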